### 3. Background

#### a. Scientific Background

Provide the scientific or scholarly background for, rationale for, and significance of the research based on the existing literature and how will it add to existing knowledge. A list of references or bibliography must be included as part of this document or uploaded separately.

Nearly 20% of postpartum women suffer from postpartum depression (PPD), a life-threatening, debilitating and costly mood disorder that emerges within a year of delivery. PPD has a substantial impact on the health of mother and child including negative maternal-infant interaction, lower likelihood of breastfeeding, and completing recommended immunizations. PPD is also associated with child behavioral problems and poorer cognitive development. The national health care costs associated with PPD in 2017 were estimated at \$2.9 billion for mothers and \$4.9 billion for their children. Importantly, the US Preventive Services Task Force recognized that PPD is preventable and issued a recommendation to refer women at increased risk of PPD (those with a history of depression prior to pregnancy or at least moderate postpartum depressive symptoms that do not meet the diagnostic threshold for PPD) to counseling services. Our team responded in a JAMA Pediatrics Editorial highlighting the urgent need to identify other evidence-based preventive interventions, such as PA interventions, that may not involve intense health care system resources.

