#### 14. Provisions to Monitor Data to Ensure the Safety of Subjects

This is required when research involves more than Minimal Risk to subjects.

The plan might include establishing a data monitoring committee and a plan for reporting data monitoring committee findings to the IRB and the sponsor. Describe:

- Who will monitor the study data for safety?

The PIs will review all safety data collected at the 3-month (T1) and 6-month (T2) follow-up surveys.

- The plan to periodically evaluate the data collected regarding both harms and benefits to determine whether subjects remain safe.

The PIs will review reported adverse events collected at the 3-month (T1) and 6-month (T2) follow-up surveys every 6 months during data collection.

- What data are reviewed, including safety data, untoward events, and efficacy data.

We will collect data on severe or life-threatening injury or illness that required hospitalization overnight in postpartum participants or their infants, whether adverse events were related to exercise, and whether adverse events resulted in persistent or significant disability or incapacitation.

- How the safety information will be collected (e.g., with case report forms, at study visits, by telephone calls with participants).

Adverse event information will be reported by participants as part of follow-up surveys.

- The frequency of data collection, including when safety data collection starts.

Adverse event information will be collected as part of the 3-month and 6-month follow-ups surveys.

- The frequency or periodicity of review of cumulative data.

Adverse event data will be reviewed by the PIs every 6 months during data collection.

- Criteria for taking action on monitoring findings (for instance, stopping rules, immediate suspension, reporting, protocol changes, changes to monitoring frequency or plan).

Serious adverse events are not anticipated in this study. If serious adverse events (adverse events that require hospitalization or results in a persistent or significant disability or incapacitation in the postpartum participant or her infant) are reported related to exercise, the PIs will report these events to the IRB and remove participants who experience serious adverse events from the study. The PIs will incorporate protocol changes, including increasing adverse event monitoring to include identification of hospitalization events in participants using the electronic health records on a more frequent basis (i.e. monthly).

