## 15. Risks and Benefits

### a. Risks to Subjects

List the reasonably foreseeable risks, discomforts, hazards, or inconveniences to the subjects related to the subjects' participation in the research. Consider physical, psychological, social, legal, and economic risks.

Patient participants: There may be some inconveniences in participating, including regularly accessing a computer, mobile device, or TV with internet access for email, survey completion, and logging in to Momzing however, participants will be informed of all the steps involved in participation before being enrolled in the intervention. Also, some of the eligibility and survey questions (i.e. PHQ-8) may trigger emotional discomfort or feelings. If it is noted that a participant has a score of 20 or higher on this section, we will follow our protocol for contacting those participants (please see Appendix U). Lastly, participants in the intervention group could experience fatigue, muscle soreness, and injury, such as a sprained ankle or strained muscle, while exercising. They can reduce these risks by proper warm-up and cool-down periods, adequate hydration, and carefully monitoring and planning their exercise.

Clinicians: The risks are minimal for clinicians participating in key stakeholder interviews as they will be asked to address identified avenues for adoption of MomZing as a resource for their patients at increased risk of postpartum depression and barriers to implantation and maintenance within clinical practice at KPNC, which should not have any risks.

Describe the probability, magnitude, duration, and reversibility of the risks.

Participants will be informed of all the steps involved in participation before being enrolled in the study including any risks. Considering the intervention is not physically invasive, the physical and psychological risks mentioned above are low in probability and magnitude.

If applicable, indicate which procedures may have risks to the subjects that are currently unforeseeable.

N/A

If applicable, indicate which procedures may have risks to an embryo or fetus should the subject be or become pregnant.

N/A

If applicable, describe risks to others who are not subjects and risks to Kaiser Permanente

N/A

b. Potential Benefits to Subjects

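### The only stated trigger for IRB reporting is a serious event reported as exercise-related, and the serious-event definition leaves out death

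*Combined protocol and SAP*

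**What the plan says.** Section 14 sets out the safety monitoring.

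- **Definition.** Serious adverse events are "adverse events that require hospitalization or results in a persistent or significant disability or incapacitation in the postpartum participant or her infant".
- **What is collected.** "We will collect data on severe or life-threatening injury or illness that required hospitalization overnight in postpartum participants or their infants". Whether the event was related to exercise, and whether it left lasting disability, are further items.
- **Source.** "Adverse event information will be reported by participants as part of follow-up surveys", at 3 and 6 months.
- **Review.** "Adverse event data will be reviewed by the PIs every 6 months during data collection".
- **Action.** If serious events "are reported related to exercise, the PIs will report these events to the IRB" and remove the affected women from the study. Protocol changes follow, among them "increasing adverse event monitoring to include identification of hospitalization events in participants using the electronic health records on a more frequent basis".

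The monitoring-committee item is answered as not applicable.

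Four other places bear on the point:

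- Section 3.a describes postpartum depression as "a life-threatening, debilitating and costly mood disorder that emerges within a year of delivery".
- Section 5.c, under Children, gives adverse-event monitoring as one reason for linking mother and baby records. Its example is injuries and their relationship with the intervention.
- Section 9.a has the study team monitor safety, deal with issues that arise and consult the PI.
- Section 15.a says that if "a participant has a score of 20 or higher on this section, we will follow our protocol for contacting those participants". The contact protocol is in Appendix U, which is not among the public documents.

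**The concern.** The women are chosen because they have raised depressive symptoms and are not in treatment (section 5.b), and the protocol itself regards the condition they are at risk of as life-threatening. Psychiatric deterioration, self-harm and death are therefore foreseeable serious events. The action rule is built around exercise injury. It passes on to the IRB only events reported as related to exercise, and it starts from a definition in which death does not appear. The study's depression scale, the PHQ-8, has no item on suicidal thoughts (section 9.a, Outcomes), so that instrument does not fill the gap.

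At stake is whether the IRB would hear of the gravest events in this population, and whether the final report would count them as serious events at all.

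**Working it through.** The plan states no figure here to reproduce. The check applies the section 14 rule, as written, to the kinds of event that matter. It gives the same result in either arm.

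| Event | In the serious-event definition? | In the survey data listed? | Stated IRB trigger? |
|---|---|---|---|
| Exercise injury with overnight admission | Yes | Yes | Yes, if reported as exercise-related |
| Psychiatric admission of the mother | Yes, through hospitalization | Yes, if overnight and she reports it | Only if reported as exercise-related |
| Life-threatening self-harm, no admission | No, unless it leaves lasting disability | No, the data are tied to an overnight admission | None, unless it leaves lasting disability and is reported as exercise-related |
| Out-of-hospital maternal death, including suicide | No | No, she cannot complete the survey | None |
| Out-of-hospital infant death | No | No, the data are tied to an overnight admission | None |

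**Do other sections supply the missing route?**

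- Section 5.c names linked records as a means of monitoring adverse events, but gives no schedule, no mention of death and no reporting step.
- Section 14 mentions an electronic-record search for hospitalizations only among the protocol changes that follow a trigger. Its reference to a more frequent basis could imply a slower routine search, but none is described. Sections 5.c and 14 therefore do not agree on whether records are a routine source.
- Section 9.a gives no criterion and no IRB report.
- The section 15.a rule responds to a questionnaire score of 20 or higher, not to an event.

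**Timing, from the plan's own intervals.** The longest wait for the next survey is 3 months. The longest wait for the next PI review is 6 months. 3 + 6 = 9 months from event to review, assuming that the survey is returned on time.

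**Non-return.** Section 9.b allows for up to 16% loss to follow-up: 0.16 × 200 = 32 women. For them, the stated source of adverse-event data can be empty. A woman who has died, or is in hospital, may be among them.

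**Exposure.** With complete follow-up to 6 months, 200 × 0.5 = 100 person-years in mothers. If the 32 women contributed no time, (200 − 32) × 0.5 = 84 person-years. The documents give no rate for admission, self-harm or death, so no expected count follows.

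**The case against.** The strongest reply is that the plan catches more than the action rule alone suggests. Much of it stands.

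- **A reader might infer that a psychiatric admission would trigger nothing.** The documents do not support that. The definition covers any hospitalization, with no psychiatric exception. An overnight admission is collected whatever its cause, and the PIs review it in both arms. What is missing is a criterion for sending it to the IRB.
- **A reader might infer that the participant alone decides relatedness.** The surveys make this plausible, but section 14 does not name who judges. Section 5.c also points to records as a source on injuries and their relationship with the intervention.
- **A reader might infer that the rule works in one arm only.** The criterion is exercise, not MomZing, and control women can exercise: section 9.b plans on 23% of them meeting the activity guidelines.
- **A reader might infer that the between-arm safety comparison becomes uninterpretable.** Section 9.b specifies no such comparison, and hospitalizations are collected regardless of attribution.
- **A reader might infer that psychiatric events would go unseen altogether.** Depression and anxiety diagnoses come from the electronic record, and health care utilization is an exploratory outcome. These are outcome data, however, with no reporting step attached.

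IRB-wide reporting policy may also apply from outside the protocol, and Appendix U may say more. Neither can be checked here, and section 14 does not cite such a policy. None of these replies provides a stated route for an out-of-hospital death of mother or infant.

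**Conclusion.** The point holds in a limited form. The only stated criterion for IRB reporting and action covers serious events reported as exercise-related, and the definition omits death and life-threatening events without admission. In either arm, a psychiatric admission is collected if self-reported and is reviewed at the next six-monthly look, but has no stated reporting criterion unless it is called exercise-related. An out-of-hospital suicide or infant death has no stated capture or reporting route.

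This is a rule that misses foreseeable events, not merely a detail left unwritten. It should be changed. Its size is a matter of coverage rather than a count: 200 mothers and their infants, at most about 100 person-years in mothers to 6 months, and a delay of up to about 9 months even where an event is collected. The conclusion rests on reading section 14 as the complete statement of the reporting rule, and on no further rule standing in the material not public.

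**What to change.** In section 14:

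1. Add death of mother or infant, and life-threatening events including self-harm, to the serious-event definition. Psychiatric admission needs no separate entry because hospitalization already covers it.
2. Have the PIs assess every serious event in both arms for relatedness to study participation and for IRB reporting, whatever the participant says about exercise.
3. State the IRB-reporting criterion separately from the removal-from-study rule. One sentence now governs both, so widening it as it stands would also widen removal. No change to the removal rule is proposed here.
4. Tabulate serious events by arm. Section 9.a says the investigators and analysts are blinded, so coded arm labels would suit.
5. When a 3- or 6-month survey is not returned, check the already linked mother and baby records, within the section 9.a limit that bars use of health information obtained after a woman withdraws authorization.
6. Reconcile section 5.c with section 14 on whether records are a routine source of adverse events or only an escalation.

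The cost is amended wording and survey items, slightly more events for the PIs to assess and report, and modest programmer time for the record checks. Sample size and the efficacy analyses are unaffected.

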## 15. Risks and Benefits

### a. Risks to Subjects

List the reasonably foreseeable risks, discomforts, hazards, or inconveniences to the subjects related to the subjects' participation in the research. Consider physical, psychological, social, legal, and economic risks.

Patient participants: There may be some inconveniences in participating, including regularly accessing a computer, mobile device, or TV with internet access for email, survey completion, and logging in to Momzing however, participants will be informed of all the steps involved in participation before being enrolled in the intervention. Also, some of the eligibility and survey questions (i.e. PHQ-8) may trigger emotional discomfort or feelings. If it is noted that a participant has a score of 20 or higher on this section, we will follow our protocol for contacting those participants (please see Appendix U). Lastly, participants in the intervention group could experience fatigue, muscle soreness, and injury, such as a sprained ankle or strained muscle, while exercising. They can reduce these risks by proper warm-up and cool-down periods, adequate hydration, and carefully monitoring and planning their exercise.

Clinicians: The risks are minimal for clinicians participating in key stakeholder interviews as they will be asked to address identified avenues for adoption of MomZing as a resource for their patients at increased risk of postpartum depression and barriers to implantation and maintenance within clinical practice at KPNC, which should not have any risks.

Describe the probability, magnitude, duration, and reversibility of the risks.

Participants will be informed of all the steps involved in participation before being enrolled in the study including any risks. Considering the intervention is not physically invasive, the physical and psychological risks mentioned above are low in probability and magnitude.

If applicable, indicate which procedures may have risks to the subjects that are currently unforeseeable.

N/A

If applicable, indicate which procedures may have risks to an embryo or fetus should the subject be or become pregnant.

N/A

If applicable, describe risks to others who are not subjects and risks to Kaiser Permanente

N/A

b. Potential Benefits to Subjects

Describe the potential benefits that individual subjects may experience from taking part in the research. Include as may be useful for the IRB's consideration, the probability, magnitude, and duration of the potential benefits. Indicate if there is no direct benefit. Do not include benefits to society or others.

Participants in the intervention arm may benefit from the intervention if our hypothesis is correct and they experience a decrease in postpartum depressive symptoms and an increase in physical activity, which may also positively impact other aspects of their life including physical (e.g. decrease in postpartum weight retention) and mental health (decrease in stress and anxiety).

c. Risks to KP

Is there anything about the nature of this study which, if revealed to the public, could put KP at risk or competitive disadvantage?  Yes  No

If "yes" describe in detail.

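### Section 14's survey criterion for adverse events is narrower than its own serious-event definition, has no item for the minor exercise harms foreseen in Section 15a, and is not aligned with the record search in Section 5c

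*Combined protocol and SAP*

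**What the plan says.** Section 15a (Risks to Subjects) expects the following physical harms: "participants in the intervention group could experience fatigue, muscle soreness, and injury, such as a sprained ankle or strained muscle, while exercising". It adds that "the physical and psychological risks mentioned above are low in probability and magnitude".

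Section 14 (Provisions to Monitor Data to Ensure the Safety of Subjects) answers the question of which data are reviewed: "We will collect data on severe or life-threatening injury or illness that required hospitalization overnight in postpartum participants or their infants". The same sentence goes on to two further items: "whether adverse events were related to exercise" and "whether adverse events resulted in persistent or significant disability or incapacitation". The information comes from participants' own reports in the 3-month (T1) and 6-month (T2) surveys.

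Further down, Section 14 defines serious events as "adverse events that require hospitalization or results in a persistent or significant disability or incapacitation in the postpartum participant or her infant". If such events are reported and are related to exercise, they go to the IRB and monitoring is stepped up, including monthly searches of the electronic record for hospitalizations.

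Section 5c (Subjects Vulnerable to Coercion or Undue Influence, entry on children) gives a second source. Mother and baby records will be linked, among other reasons, to monitor safety by finding injuries that a doctor treated or that led to a hospital stay, and to judge their relation to the intervention.

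Section 9b (Data Analysis) specifies no comparison of adverse events between arms.

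**The concern.** The event that Section 14 describes for collection is at the far end of severity, while the harms that Section 15a expects are at the near end. The section also sets a higher bar for collecting an event than for calling it serious. The rule for reporting to the IRB acts on events that are reported, so an event that is serious by definition but outside the survey criterion may not trigger it.

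The trial is meant to inform adoption of MomZing at KPNC and possibly in other regions (Section 2). An adverse-event table that is empty because of how the question was put would not show that the program is safe, and it would not support the statement that the risks are low. Injury is also a plausible reason for a woman to stop using the videos or to be less active at T1, and an unrecorded injury cannot be examined as such.

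**Working it through.** The plan gives no figure on this point, so the main check sets the passages side by side.

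**Step 1: three definitions against six kinds of event.** Inputs are the Section 14 collection criterion, the Section 14 serious-event definition and the Section 5c record search.

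| Event | Survey criterion (14) | Serious (14) | Record search (5c) |
|---|---|---|---|
| Severe, overnight stay | yes | yes | yes for injury; illness not named |
| Admission that is not overnight or not severe | no | yes | yes for injury; illness not named |
| Lasting disability, no admission, seen by a doctor | unclear | yes | yes for injury; illness not named |
| Lasting disability, no admission, not seen by a doctor | unclear | yes | no |
| Sprain or strain seen by a doctor, no admission | no | no | yes |
| Fatigue, soreness, self-managed sprain or strain | no | no | no |

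The second row is a direct mismatch inside Section 14 and needs no outside assumption. The last row is a gap in both sources. Each *yes* in the last column holds only if the Section 5c search is actually run as a routine safety source.

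**Step 2: the disability item.** The relatedness and disability items speak of adverse events without further limit. They may be separate questions, or follow-ups to the hospitalized event named just before them. The text allows both, hence *unclear* in rows three and four.

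**Step 3: Section 5c against Section 14.** Section 14 names participant report as the collection route. It mentions the electronic record only in the step taken after exercise-related serious events, as a search for hospitalizations. It does not list the wider injury search of Section 5c.

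**Step 4: illustrations.** The arm size of 100 and the 16% loss to follow-up are from Section 9b. All injury and hospitalization rates are assumptions.

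- *What the overnight criterion would catch.* With n women, injury risk p and share h of injuries with an overnight stay, expected injuries are n·p, expected captures are n·p·h, and the chance of recording any is 1 − (1 − p·h)^n. At n = 100, p = 10% and h = 1%: 10 injuries, 0.1 captured, and 1 − 0.999^100 = 9.5%. Over p = 5% to 30% and h = 0% to 5%: 5 to 30 injuries, of which 0 to 1.5 are captured.
- *What both sources would miss.* With u the share of injured women who see no doctor, the number missed is n·p·u. The documents give no value for u. At p = 10%, u from 0 to 1 gives 0 to 10 women.
- *What zero events would show.* For 0 of 100, the one-sided 95% upper limit is 1 − 0.05^(1/100) = 2.95%. For 0 of 84, where 84 = 100 × (1 − 0.16), it is 3.50%. These limits apply to overnight hospitalized events only.
- *What recording would give.* For an assumed 10% against 3%, the 95% half-width is 1.96·√(0.10·0.90/100 + 0.03·0.97/100) = 6.8 points with 100 per arm, and 7.4 points with 84 per arm.

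**The case against.** The strongest reply is Section 5c. Its record search requires neither severity nor an overnight stay, it covers mother and baby, and it includes relation to the intervention. Section 9a also collects health care utilization from the electronic record and the surveys. Three stronger readings are therefore tempting but unsupported:

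- A reader might infer that an outpatient fracture with lasting disability would never be recorded. Such an injury would ordinarily be treated by a doctor, which is what Section 5c plans to find.
- A reader might infer that no exercise-injury rate could be reported in either arm. Treated injuries could be counted from records; only untreated ones have no stated source.
- A reader might infer that every injury without an overnight stay goes unrecorded. That would assume that no injured woman saw a doctor.

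It can also be said that Section 14 lists disability in its own right; that its wording about more frequent record searches may imply a base frequency, although none is stated; that Section 14 is a short summary on an IRB form, with the actual survey items in Appendices M to P, which are not in the supplied text; and that women with cardiac, orthopedic, syncope or asthma problems are excluded, so minor harms may be few and no primary estimate is affected.

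All of this limits the point without removing it. The severe-and-overnight wording is still narrower than the section's own definition, no section states an item for untreated harms, and Sections 5c and 14 still describe different safety sources.

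**Conclusion.** The point holds in a limited form. Two parts are firm on the text. First, the survey criterion in Section 14 leaves out hospitalizations that its own serious-event definition includes. Second, nothing in the document provides for recording fatigue, soreness or self-managed sprains and strains, although Section 15a foresees them. A third part is conditional: a disabling event without admission may be missed by the surveys, depending on how the disability item is asked.

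The loss is confined to untreated or self-managed exercise injuries and to serious events that reach neither the survey criterion nor the record search. Its size cannot be derived from the documents; the 0 to 10 women per 100 above rests on an assumed 10% injury rate and an unknown share seeing a doctor. If the record search is not run routinely, treated injuries without an overnight stay would join the gap. If the survey forms already ask about any injury, the remedy is to say so in Section 14. The primary analyses are not affected; what suffers is the safety evidence for adoption.

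**What to change.** - In the T1 and T2 surveys, for both arms, ask first about any injury or pain that limited activity or occurred during exercise, for the mother and for the infant if held.
- Then ask about any hospitalization and about any persistent disability as two separate items, so that each branch of the serious-event definition can be met on its own. Word the Section 14 collection criterion to match.
- Reconcile Section 14 with Section 5c by naming the record-based injury search as a routine safety source and stating how often it is run.
- Add to Section 9b a table of counts by arm, with a 95% interval for the difference.

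The cost is two or three items in surveys that are already sent, one table and a few lines of text. The downside is slightly longer surveys and more minor events to list.
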